Assesment of Post-stroke Elbow Flexor Spasticity in Response to Passive Stretch in Different Forearm Positions

Brief Title: Assessment of post-stroke elbow flexor spasticity in different forearm positions

Protocol ID: 21.02.2018-84

Date of the document: February 21, 2018

Background

Determination of which muscle is more spastic before injection of the botulinum toxin, and subsequently the application of the targeted treatment to that muscle is expected to result in more improvement in stroke patients with spasticity. From the view of point of post-stroke elbow flexor spasticity, there are three main muscles that contribute to spasticity; musculus biceps brachii, musculus brachialis and musculus brachioradialis (1). However, there are conflicting results regarding which muscle or muscles should be selected as treatment target in post-stroke elbow spasticity (2,3). Here the question is how to select the right muscle. The superficiality of the biceps brachii muscle makes it an easy target for botulinum toxin injection (2). In dynamic electromyography studies, it has been reported that brachioradialis muscle is the most common contributor one to elbow flexion spasticity, followed by biceps brachii muscle (3). In the diagnostic selective nerve blocks, the brachialis muscle has been reported to be foreground (2).

It is known that the muscles that flex elbow in healthy individuals change according to forearm position (4). While the biceps brachii flexes the forearm in supination, the brachioradialis flexes the forearm in the neutral position. The brachialis muscle acts as a primary flexor muscle when the forearm is in pronation, but it flexes the elbow in all forearm positions (4). In the light of this anatomical and biomechanical knowledge, can the target muscle be selected by examination instead of other methods such as electromyography where equipment is required and the evaluation period is relatively long? Can semi-quantitative methods such as Modified Ashwort Scale (MAS) (5) and Modified Tardieu Scale (MTS) (6) be used to assess the severity of spasticity provide reliable information regarding the muscle or muscles that contribute to elbow flexor spasticity? In this study, hypothesis is that the severity of the post-stroke elbow spasticity

differs depending on the forearm position that is one of the determinants which elbow flexor muscle to be more active in healthy subjects.

Aim

The aim of this study is to investigate whether the severity of spasticity differs depending on the forearm position.

Methods

Study design

This study is a single group, observational and cross-sectional study. Participants who meet the inclusion criteria and give written informed consent will be included in the study. This study was approved by the non-interventional Ethics Committee of Faculty of Medicine of İzmir Katip Çelebi University with approval number of 21.02.2018-84.

Setting

Subjects will be recruited based on identification of stroke patients with elbow flexor spasticity who present to outpatient or inpatient clinics of Physical Medicine and Rehabilitation (PMR) Department of İzmir Katip Çelibi University Atatürk Training and Research Hospital. All assessments will also be performed at the department of PMR of İzmir Katip Çelibi University Atatürk Training and Research Hospital.

Selection criteria

First the physician will ask potential participants (patients affected by stroke whose elbow is in flexion position) if they are interested in including the study. If they are, physician will assess them in terms of following inclusion and exclusion criteria:

- Elbow flexor spasticity
- Grade 1 to 3 spasticity measured with MAS (5)
- To agree to participate in the study

Exclusion Criteria

- <18 years old
- Pregnancy
- Botulinum toxin injection within the last three months
- Presence of elbow contracture
- History of operation to spastic upper extremity
- Spasticity due to other causes other than stroke
- Do not agree to participate in the study

In case of voluntary participation, patients will be asked to sign written informed consent. Immediately after, another study physican will perform the assessments.

Randomization and blinding

This study is a non-randomized and unblinded study.

Outcome assessment and data collection

After recording general demographic information (age, gender) and clinical patient characteristics (stroke type and side, disease duration, spontaneous elbow angle in upright position and Brunnstrom stage of motor recovery (7), participants will be assessed in terms of elbow flexor spasticity with MTS (6).

Primary outcome: Dynamic component of spasticity measured with MTS

The MTS is a spasticity scale that evaluates the velocity-dependent muscle reaction (6). Slow passive stretching (V1) evaluates passive range of motion (R2). To grade the quality of muscle reaction, passive stretch is performed by taking into account the falling speed of the limb segment under gravity (V2). The quality of muscle reaction ranges from 0 to 4. Grade 0 represents no spasticity and grade 4 represents severe spasticity. The angle of muscle reaction (R1) [the point of catch in response to spasticity in case of quality of muscle reaction to be score of 2 or higher] is evaluated by stretching the limb segment as fast as possible (V3). The difference between the R2 and R1 (R2-R1) represents the dynamic component of spasticity (spasticity angle). A big difference suggests spasticity while the low difference suggests muscular contracture.

Procedure

In this study, slow controlled motion, muscle reaction to fast stretching, quality of muscle reaction and dynamic component of spasticity will be assessed separately in the pronation, neutral and supination positions of forearm unlike the classical MTS assessment. Dynamic component of spasticity is selected as the primary outcome measure which best represents the spastic component of hypertonia. The MTS measurement will be performed while the patient is in sitting position on an examination bed, and his/her shoulder is adducted as described elsewhere (8), but differently, in three different forearm positions . Patients were asked to relax as much as possible. First, R2 will be measured with slow controlled maneouvre at the speed of V1, and than muscle reaction angle and quality of muscle reaction will be measured at the speed of V2 which will be extrapolated from healthy side of the patient. R2 and R1 will be measured with a standard goniometer (Baseline®, Fabrication Enterprises Inc, Newyork, USA) by two physician. One of them (A) will first position the limb, and than A will ask other one (B) to hold the positioned limb. Immediately after, while the B is holding the positioned limb, A will measure the elbow

angle. To measure the R1 and R2 in supination position of forearm; axis of goniometer will be placed in the lateral epicondyle of humerus, stationary arm will be aligned towars the center of acromion process and moving arm will be aligned towards the styloid process of radius (9). To measure the R1 and R2 in neutral position of forearm; axis and stationary arm placement will not change, but moving arm will be aligned towards the long finger by positioning the wrist in a neutral position. To measure the R1 and R2 in pronation position of forearm; axis and stationary arm placement will also not change, but moving arm will be aligned towards the styloid process of ulna. The end position is 180 degrees of full elbow extension. Because the R1 and quality of muscle reaction are evaluated at the same stretching speed (V2), these two measurements will be performed at the same time. In case of quality of muscle reaction to be score of 0 or 1, R1 and R2 will be accepted equal.

Sample size and power

The primary outcome of this study is to detect the differences in dynamic component of poststroke elbow flexor spasticity in different forearm positions. As far as we know, no such study has been conducted to date. Therefore, a priori sample size calculation for this study was based on some arbitrary assumptions including a moderate effect size (0.25) with correlation among repeated measures of 0.5 and epsilon of 1 for one way repeated measure ANOVA . Based on these assumptions with a Tip I error rate of 5.0 and 90% power, to reject the null hypothesis of no difference between dynamic components of elbow flexor spasticity in three different forearm positions, at least 36 patients were required. Sample size calculation was performed with G*Power software (G*Power, version 3.1.9.2, Germany).

Statistical analyses

Firstly a descriptive analyses of demographic and clinical characteristics of patients will be performed. For the primary hypothesis, a one way repeated measure analysis of variance will be performed to compare differences in dynamic component of elbow flexor spasticity within three forearm positions. However, if the assumptions for one way repeated measure ANOVA are not met, Friedman's two way analysis of varience with Bonferroni correction will be performed. A level of 0.05 for statistical significance will be fixed.

Reporting of results

The results of this study will be presented at national and/or international meetings and will be pulished in journals.

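### The testing order of the three forearm positions is not set, balanced or stated to be recorded, so under one common order drift in R2−R1 could not be separated from position

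*Combined protocol and SAP*

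**What the plan says.** The Procedure section states that the Modified Tardieu measures "will be assessed separately in the pronation, neutral and supination positions of forearm unlike the classical MTS assessment", and it describes the set-up "as described elsewhere (8), but differently, in three different forearm positions". The three positions are therefore this study's own departure from the cited method.

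The only sequence the section fixes is within a position: "First, R2 will be measured with slow controlled maneouvre at the speed of V1", followed by the reaction angle R1 and the reaction quality at V2.

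The positions are listed twice, in opposite directions. The sentence above runs pronation, neutral, supination. The goniometry starts at the other end ("To measure the R1 and R2 in supination position of forearm; axis of goniometer will be placed in the lateral epicondyle of humerus"), passes through neutral and finishes with pronation ("To measure the R1 and R2 in pronation position of forearm; axis and stationary arm placement will also not change"). Neither list is presented as a testing order.

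Under Randomization and blinding the protocol says only: "This study is a non-randomized and unblinded study". Under Outcome assessment and data collection, the variables named for recording begin "After recording general demographic information (age, gender) and clinical patient characteristics (stroke type and side, disease duration" and go on to the resting elbow angle and Brunnstrom stage. Testing order is not among them. No interval between positions is given.

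The Statistical analyses section compares R2−R1 across the three positions by one-way repeated-measures ANOVA, with the Friedman test as fallback. Neither contains a term for order.

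**The concern.** The comparison is entirely within patient. Using each patient as their own control removes differences between patients, but not changes during the session. Each position needs at least one slow and one faster stretch of the same elbow, so a patient has at least six stretches, with holds while the angle is read. The outcome is a velocity-dependent muscle reaction that might change with repetition. Drift shared equally by R2 and R1 cancels in the difference; drift that affects one more than the other does not.

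If all patients follow one order, position and place in the sequence are the same variable. Unshared drift could then produce a significant result with no position effect, or hide a real one, and the collected data could not show which had happened. If the order varies from patient to patient without being noted, some bias may remain and cannot be adjusted for.

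**Working it through.** **Inputs from the protocol (Sample size and power).** Effect size f = 0.25, correlation ρ = 0.5, epsilon 1, three measurements, 5% type I error, 90% power, and "at least 36 patients were required".

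**Assumed inputs.** The size and shape of any drift, in SD units of R2−R1. The documents give none.

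**1. The plan's own figure.** For one group measured m = 3 times, λ = f²·N·m/(1−ρ), which equals N·Σ(μ−μ̄)²/(1−ρ), with 2 and 2(N−1) degrees of freedom.
- N = 36: λ = 0.0625 × 36 × 3 / 0.5 = 13.5; df 2 and 70; power 90.6%.
- N = 35: power 89.8%.

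So 36 is reproduced. With equally spaced means, f = 0.25 corresponds to a step of 0.25/√(2/3) = 0.306 SD between adjacent positions. Half of that is 0.153 SD.

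**2. Can order be separated from position?** A model with patient, position and measurement-order terms for 36 patients has rank 38 under one common order, the same as patient and position alone (36 + 2). Order therefore cannot be estimated apart from position. With all six orders used equally the rank is 40, and both can be estimated.

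**3. One common order, no true position effect.** The drift takes the place of the means in λ.
- Linear drift (0, d, 2d): Σ(μ−μ̄)² = 2d². At d = 0.10, λ = 36 × 0.02 / 0.5 = 1.44.
- Plateau drift (0, d, d): Σ(μ−μ̄)² = (2/3)d². At d = 0.10, λ = 36 × 0.00667 / 0.5 = 0.48.

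| Drift d (SD per step) | False positives, linear | False positives, plateau |
|---|---|---|
| 0.05 | 7.7% | 5.9% |
| 0.10 | 16.7% | 8.6% |
| 0.153 | 34% | 14.0% |

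The Friedman test behaves similarly (simulation, 40,000 replicates): at d = 0.10 and 0.153, 14.2% and 26.9% for linear drift, and 8.1% and 11.9% for plateau drift.

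**4. One common order, drift opposing the planned effect, d = 0.10.**
- Linear: the step shrinks to 0.306 − 0.10 = 0.206, Σ(μ−μ̄)² = 0.0850, λ = 6.12, power 57.4%.
- Plateau: Σ(μ−μ̄)² = 0.1329, λ = 9.57, power 77.9%.

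Without drift the power is 90.6%.

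**5. Order varying, unrecorded, between the two listed sequences, d = 0.10 (simulation).** An 18/18 split gives 4.7% (linear) and 5.9% (plateau). A 27/9 split gives 7.5% and 6.3%.

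**6. Six balanced orders, six patients each, planned ANOVA without an order term (simulation).**

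| Drift d | False positives, linear / plateau | Power, linear / plateau |
|---|---|---|
| 0.05 | 4.9% / 5.1% | 90.4% / 90.7% |
| 0.10 | 4.8% / 4.9% | 90.3% / 90.5% |
| 0.153 | 4.3% / 4.8% | 89.4% / 90.4% |
| 0.306 | 2.9% / 4.1% | 85.8% / 89.4% |

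An order term (error df 70 to 68) holds power at 90.4–90.8% throughout.

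**7. Scale.** If the SD of R2−R1 is 20 degrees (assumption; range 15–30), 0.10 SD is 2 degrees (1.5–3).

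**The case against.** The strongest reply is that the harm is hypothetical. It needs three things together, none shown in the documents: a common or strongly unbalanced order, drift that R2 and R1 do not share, and drift that is steady or large. For small or plateauing drift the inflation is slight, and the 34% figure requires drift of half the planned effect. This stands, and it limits the conclusion to a vulnerability.

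Second, the list of recorded variables covers background characteristics taken before the spasticity test. R1 and R2 are not in it either, and no case report form is in the documents. So the absence of order from that list is weak evidence that it will go unrecorded. The supportable statement is that the protocol does not say it will be recorded. The cost of unrecorded variation is also modest in the split-order illustration, at about 5–8% false positives.

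Third, the Procedure sets R1 equal to R2 when reaction quality is 0 or 1. Patients scoring that low in all three positions contribute no drift. If 20%, 33% or 50% of patients were like this (assumed; SD is that of the remaining patients), linear drift of 0.10 SD under a common order would give about 14%, 12% or 10% false positives instead of 17%. At 0.153 SD the figures are about 28%, 23% or 17% instead of 34%. The inflation shrinks but does not vanish.

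Two other defences fail. Being non-randomized describes a single-group observational design; the order of measurements is still the investigators' choice. The cited source for the scale may cover spacing between stretches, but it cannot be assumed to set an order for positions that this study adds.

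**Conclusion.** The concern holds and should be fixed. The omission is plain from the text: no testing order, no balancing, no interval between positions, and no statement that order will be recorded. Under one common order, confounding of position with unshared drift is complete and cannot be repaired once the data are collected.

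How much this would matter is unknown. All drift sizes and shapes used here are assumptions, and the calculations take 36 patients, ρ = 0.5 and, apart from the check of the score-0/1 rule, drift in every patient. Within those limits, small or plateauing drift does little and steady drift does more. The sample size calculation is not in error.

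**What to change.** In Procedure, assign each patient one of the six orders of pronation, neutral and supination from a list generated in advance in blocks of six. That gives six patients per order at 36. Keep the interval between positions the same and record the order used. Because 36 is a minimum, continue the list in blocks beyond it; an incomplete last block does no harm (about 3–5% false positives at 38 to 41 patients).

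The planned ANOVA or Friedman test can remain primary. In simulation, balance kept both at about 5% false positives or below under additive drift of either shape. Two additions are optional: a measurement-order term (first, second, third) in a linear model with patient effects, which recovers power if drift is large, and a sensitivity model that includes the preceding position.

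The cost is a sequence list, one data field and a slightly more complex routine for the two physicians, with no extra patients, staff or visits. The Procedure text would need revising, and the non-randomized wording should be clarified so that it is not read as ruling out an allocated measurement order.

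One limit remains: balancing reduces unequal carry-over but does not remove it. With an assumed carry-over of −0.2, 0 and +0.2 SD by preceding position, false positives are about 9% with balanced orders, against about 21% with everyone tested in the order pronation, neutral, supination.

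### Bonferroni is attached only to the Friedman fallback and no pairwise rule follows the ANOVA; one Holm rule for both branches would be a cheap, minor improvement

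*Combined protocol and SAP*

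**What the plan says.** The Aim is an overall question: "The aim of this study is to investigate whether the severity of spasticity differs depending on the forearm position". The Sample size and power section matches it. The null hypothesis is no difference among the three positions, the effect size is 0.25 "with correlation among repeated measures of 0.5 and epsilon of 1", and with 5% type I error and 90% power "at least 36 patients were required".

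The Statistical analyses section states that "a one way repeated measure analysis of variance will be performed to compare differences in dynamic component of elbow flexor spasticity within three forearm positions". If the ANOVA assumptions fail, Friedman's "two way analysis of varience with Bonferroni correction will be performed". It then adds: "A level of 0.05 for statistical significance will be fixed".

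That is all the plan says on multiplicity. After the ANOVA it names no pairwise comparison and no correction. After Friedman it names a correction, but neither the pairs nor the pairwise test.

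**The concern.** Friedman's test is a single overall test, so a Bonferroni correction beside it makes sense only if pairwise comparisons are meant to follow. The same follow-up is just as natural after the ANOVA, yet nothing is said there. The two branches would treat the same question differently, and after the ANOVA the rule could be chosen once the data are known, in a study that is unblinded.

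The follow-up has practical interest. The Background asks "can the target muscle be selected by examination instead of other methods" and links supination, neutral and pronation to different flexor muscles. A significant overall test shows only that some position differs; which one differs is what bears on that question.

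There is also a choice of method. Where Bonferroni is named, I read it as three pairwise tests at 0.05/3 = 0.0167 each. That is valid, but a step-down rule on the same tests is at least as powerful with the same error control.

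**Working it through.** **Inputs.** From the documents: three positions, alpha 0.05, f = 0.25, correlation 0.5, epsilon 1, n = 36. Assumed, because the documents do not give them: normal data with SD 1, and two mean patterns that both give f = 0.25.
- Equally spaced means -0.306, 0, 0.306: f = 0.306 × √(2/3) = 0.25.
- One position 0.530 away from the other two: f = 0.530 × √(2/9) = 0.25.

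With correlation 0.5 the SD of a paired difference is √(2 × (1 - 0.5)) = 1. The standardised pairwise differences are therefore 0.306 (adjacent), 0.612 (extreme) and 0.530 (one position differs).

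**Step 1: the plan's own figure.** Noncentrality = n × 3 × f² / (1 - correlation) = 36 × 3 × 0.0625 / 0.5 = 13.5, with F on 2 and 70 degrees of freedom. Power is 0.906 at n = 36 and 0.898 at n = 35. The minimum is 36, as stated.

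**Step 2: why Holm cannot lose to Bonferroni.** Holm orders the three p-values and compares them in turn with 0.05/3 = 0.0167, 0.05/2 = 0.025 and 0.05, stopping at the first failure. Bonferroni uses 0.0167 throughout. Every Holm threshold is at least 0.0167, so each pair that Bonferroni declares is also declared by Holm, provided both use the same p-values and the same gate, if any. In simulation (50,000 datasets per setting) Holm found fewer pairs in none.

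**Step 3: family-wise error.** Under the global null, Holm and Bonferroni make at least one false declaration in exactly the same datasets, because the first step is the same: 0.046 with paired t and 0.042 with Wilcoxon. Holm's error was at most 0.049 in every setting simulated.

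**Step 4: power per true pair at n = 36** (40,000 datasets per setting, no omnibus gate).

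| Pair | Paired t: Bonferroni | Paired t: Holm | Wilcoxon: Bonferroni | Wilcoxon: Holm |
|---|---|---|---|---|
| Adjacent, equally spaced | 0.26 | 0.34 | 0.24 | 0.32 |
| Extreme, equally spaced | 0.870 | 0.876 | 0.848 | 0.854 |
| One position differs | 0.74 | 0.78 | 0.71 | 0.75 |

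With paired t and equal spacing, the mean number of true pairs found rises from 1.40 to 1.56. With one position different, both true pairs are found in 68.0% of datasets against 61.4%.

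**Step 5: the sharper rule.** If two of the three equalities between means hold, so does the third. Once one pair truly differs, at most one true null remains, so the other two pairs can each be tested at 0.05. Power with paired t is then 0.42 (adjacent), 0.88 (extreme) and 0.82 (one differs). Holm's declarations are a subset of this rule's, so its gain over Bonferroni lies between zero and that of the sharper rule. For the sharper rule the gain is 0.06 to 0.39 true pairs per study as the correlation runs from 0.3 to 0.7 and the middle mean is moved.

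Transitivity is less secure for rank tests. The Procedure also puts values at exactly zero: "In case of quality of muscle reaction to be score of 0 or 1, R1 and R2 will be accepted equal". With an assumed 40% of values at zero, Wilcoxon power for adjacent pairs is 0.16-0.19 (Bonferroni) against 0.28-0.32 (sharper rule), and Holm lies between. Holm needs no transitivity.

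**The case against.** **Nothing the plan sets out to test is affected.** This stands. Aim, null hypothesis and sample size are all omnibus, and no pairwise objective is stated. A reader might infer that the primary conclusion or the 36 patients are in doubt; the documents do not support that.

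**Error is not shown to be inflated.** A reader might infer a family-wise error of about 12%. That figure (0.123 simulated) arises only if three pairs are tested at 0.05 regardless of the omnibus result, which the plan does not propose. Unadjusted pairs tested only after a significant Greenhouse-Geisser F give 0.047.

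**That gated rule is a real rival.** Under sphericity its paired t power is 0.43, 0.90 and 0.84 for adjacent, extreme and one-differs pairs, above Holm's 0.34, 0.88 and 0.78. This stands as a cost of Holm in the ANOVA branch. The advantage does not carry over to Friedman with Wilcoxon pairs: 0.39, 0.79 and 0.75 against Holm's 0.32, 0.85 and 0.75. The plan does not specify the gated rule either.

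**The comparison with Bonferroni is conditional.** The plan does not name the pairwise test. If rank-sum comparisons were meant, Bonferroni on those declared a pair that even the sharper Wilcoxon rule missed in 2.0% to 2.5% of datasets. The guarantee in Step 2 therefore holds test for test, not for any choice of test.

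**Bonferroni has something to offer.** It comes with matching simultaneous confidence intervals; Holm has no simple equivalent. Nor can the power difference be priced in extra patients for the ANOVA branch, because the plan names no Bonferroni step there.

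**Conclusion.** A minor point and a cheap improvement. The plan leaves the pairwise follow-up unspecified after the ANOVA and corrects it only after Friedman; one stated rule would serve both. Replacing Bonferroni by Holm on the same tests gains about 8 percentage points of power for an adjacent pair, 4 when one position differs and under 1 for the extreme pair, with family-wise error held at 0.05. These sizes rest on normal data, the plan's f = 0.25 and correlation 0.5, and the assumed mean patterns. That Holm loses no pair to Bonferroni on identical p-values, and its error control, rest on none of these. Bonferroni in the Friedman branch is valid as it stands; Holm is a better option, not the correction of an error.

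**What to change.** Keep the omnibus test (repeated measures ANOVA or Friedman) at 0.05 as the primary test. Replace the Bonferroni phrase by one rule for both branches, for example:

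*The three pairwise comparisons between forearm positions (paired t-test after the ANOVA; Wilcoxon signed-rank test after Friedman) will be tested with Holm's procedure, with two-sided thresholds 0.0167, 0.025 and 0.05. The conclusion on the primary hypothesis rests on the omnibus test. Pairwise differences in degrees will be reported with 95% confidence intervals labelled as unadjusted.*

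In the ANOVA branch the sharper rule (0.0167, then 0.05 for both remaining pairs) is an option, since equality of means is transitive.

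The cost is a few sentences, with no patients or data. The downsides, beyond the power cost relative to gated unadjusted pairs, are:
- A pair can be declared when the omnibus test is not significant: at f = 0.25 in about 1% of datasets (ANOVA) and 9% (Friedman with Wilcoxon). The reverse occurs in about 2-3%. Hence the sentence that the primary conclusion rests on the omnibus test.
- An unadjusted interval can exclude zero for a pair that is not declared. Under the global null with paired t this happens in at least 0.123 - 0.044 = 0.079 of datasets, taking both rates from the same simulation run. Hence the label.
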